6.3.4 Subgroup analyses

The primary outcome will be analyzed for subgroups defined by the stratification factors for randomization:

- Risk for readmission (HOSPITAL score of 4 or 5 vs ≥6)
- Clinical site
- Diabetes
- Chronic heart failure
- COPD
- Cancer

CTU Bern	SAP for TARGET-READ phase 2	05.03.2019
	Version 1.0	Page 22 27

- Living place (nursing home vs rest)
- Living status (alone vs rest)
- Health insurance (Semi-private and private vs rest)

Table 9: Derivation of subgroups

Subgroup	eCRF sheet	Variable	Categorization
HOSPITAL score	Eligibility	hosp_score_simple	if hospital_change==no: hosp_score_simple > 5
	Baseline Characteristics	hosp_change	else:
		hosp_score_simple_2	hosp_score_simple_2 > 5
Clinical site	-	record_id	substr(record_id,1,3)
Diabetes	Index Diagnosis	comorbidities__5	comorbidities__5==checked
Chronic heart failure	Index Diagnosis	main_dx_at	main_dx_at==Heart failure or
		comorbidities__9	comorbidities__9==checked
COPD	Index Diagnosis	main_dx_at	main_dx_at==COPD exacerbation or
		comorbidities__7	comorbidities__7==checked
Cancer	Index Diagnosis	main_dx_at	main_dx_at==Neoplasm or
		comorbidities__8	comorbidities__8==checked
Living place	living_type	Categorical: Home, Protected apartment, Nursing home, Other, Unknown	living_type==Nursing home
Living status	living_st	Categorical: With spouse/partner, With another person, Alone, Unknown	living_st==Alone
Health insurance	insur	Categorical: Base, Base+compl, Semi-private, Private, Other, No insurance	insur==Semi-private or insur==Private

Subgroups will be analyzed using regression models with the treatment group, the subgroup and their interaction and the stratification factors used at randomization as covariates. If possible, a binomial model with identity link function will be used and the effects will be reported as risk differences with 95% CIs. Otherwise, a Poisson model with identity link and robust standard errors (leading to risk differences) or a binomial model with logit link (leading to odds ratios) will be considered. Models with and without interaction will be compared using a likelihood ratio test and the p-value will be reported as p-value for interaction. Results will be presented in a forest plot.

As a secondary analysis, subgroups will be categorized (according to Table 9) and analyzed using Mantel-Haenszel methodology. A risk difference will be shown for each subgroup with both a lower one-sided and a two-sided 95% CI. The p-value from a Mantel-Haenszel test of homogeneity will be presented. The Mantel-Haenszel subgroup analyses will not be stratified for the factors used at randomization.

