1.2 Objectives

The primary objective is to evaluate the effect of a transitional care intervention (“TARGET” intervention) prioritized to higher-risk medical patients on the composite of 30-day unplanned readmissions and death.

Secondary objectives are to evaluate:

- the effect of a targeted transitional care intervention to higher-risk medical patients on hospital utilization, medication adherence, patient’s perspective on quality of transition of care and time to readmission or death (whatever comes first),
- the effect of a targeted transitional care intervention on the primary outcome in subgroup population of patients with intermediate (simplified HOSPITAL score of 4 or 5) compared to high risk of readmission (simplified HOSPITAL score ≥ 6), who suffer from common chronic diseases (diabetes, chronic heart failure, COPD or cancer), and according to living place, living status and health insurance,
- the cost-effectiveness of the transitional care intervention.

2 Study methods

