5.5.3 Index diagnosis

Information about the index diagnosis is collected on eCRF “Index Diagnosis”.

Table 5: Index diagnosis and comorbidities.

Description	Variable	Type
Main diagnosis category*	main_dx_at	Categorical: Heart failure, Acute ischemic heart disease, Arrhythmia, Venous thromboembolism, Stroke/TIA, COPD exacerbation, Pneumonia, Other infection, sepsis, Gastro-intestinal disorder, Liver disorder, Renal disorder, Nutritional or metabolic disorder, Adverse drug event, Neoplasm, Epilepsy, Other
Secondary diagnoses and comorbidities*		
Chronic heart failure	comorbidities__1	Binary: Unchecked, Checked
Coronary disease	comorbidities__2	Binary: Unchecked, Checked
Atrial fibrillation	comorbidities__3	Binary: Unchecked, Checked
Peripheral artery disease	comorbidities__4	Binary: Unchecked, Checked
Diabetes	comorbidities__5	Binary: Unchecked, Checked
Dementia	comorbidities__6	Binary: Unchecked, Checked
COPD	comorbidities__7	Binary: Unchecked, Checked
Active cancer	comorbidities__8	Binary: Unchecked, Checked
Chronic renal failure	comorbidities__9	Binary: Unchecked, Checked
Liver cirrhosis	comorbidities__10	Binary: Unchecked, Checked
Drug or Alcohol Abuse	comorbidities__11	Binary: Unchecked, Checked
Epilepsy	comorbidities__12	Binary: Unchecked, Checked
Any treated psychiatric disease	comorbidities__13	Binary: Unchecked, Checked
Letter of discharge has been collected	letter_disch_late	Binary: No, Yes

*Main and secondary diagnoses are also documented as free text (variables main_dx and dx_1_dx20), which will be listed only.

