6.7 Quality control

A second statistician will reproduce the analysis of the primary outcome (for both the FAS and the PPS) based on the exported data. The risk difference and the 95% confidence interval should not differ by more than 0.01, the p-value by 0.001. Otherwise, the reason for the difference will be determined and a consensus must be reached.

7 Changes from the protocol

The SAP is consistent with principle features of the statistical methods described in the protocol. The following deviations were made:

Table 10: Changes from protocol

Header	Change	Reason
Blinded analysis	Blinded analysis not implemented	The allocation can immediately be seen from the eCRFs because only patients in the intervention group have follow up phone calls. It would therefore need an extra statistician that carefully prepares the data so that it is not possible to see the allocation. Given the open-label nature of the study and the straightforward analysis this additional effort seems not to be justified.
Secondary outcome "Medication adherence: 4-item Morisky Medication Adherence Scale (MMAS-4)".	Removed	High license fees would incur
Secondary endpoint "Number of planned hospital readmissions" and "Total number of planned days of hospitalizations"	Added	Information about the planned readmissions is of interest but was not considered in the protocol.
Test for the analysis of primary and binary secondary outcome	Stratified Cochran-Mantel-Haenszel test instead of simple chi-squared test	Stratification factor should be considered in the analysis
Subgroup HOSPITAL score	Categories 4 or 5 vs ≥ 6 instead of 5 or 6 vs ≥ 7	Categories correspond to stratification of the randomization
Subgroup clinical site	Added	Used as stratification factor in randomization
Subgroups cancer, living place, living status and health insurance	Added	Of interest, not mentioned in protocol

References

¹ Clinical trial protocol: Transition care intervention targeted to high-risk patients to reduce readmission (TARGET-READ): A randomized controlled trial, Version 1.1, 13.02.2018

² SOP Data preparation and programming, CS_STA_SOP_05, version 02, 15.08.2015

³ SOP Statistical data validation, CS_STA_SOP_02, version 02, 15.08.2015

⁴ Klingenberg, B. 2014. A new and improved confidence interval for the Mantel–Haenszel risk difference. *Statistics in medicine*, 33(17): 2968.

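### Table 9 derives the chronic heart failure subgroup from the checkbox that Table 5 assigns to chronic renal failure

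*SAP*

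**What the plan says.** The secondary objectives in SAP section 1.2 include the effect on the primary outcome in patients "who suffer from common chronic diseases (diabetes, chronic heart failure, COPD or cancer"). Section 6.3.4 lists chronic heart failure among the nine subgroups, and Table 9 gives the derivation of each.

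For chronic heart failure, Table 9 names the eCRF sheet Index Diagnosis and joins two conditions: "main_dx_at==Heart failure or" followed by "comorbidities__9==checked". The code ending in 9 also stands in the variable column of the same row.

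Table 5 in section 5.5.3 is the SAP's list of variables for that eCRF sheet. It labels `comorbidities__9` as "Chronic renal failure" and gives "comorbidities__1" as the variable for chronic heart failure.

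Section 6.3.4 then adds a second analysis in which "subgroups will be categorized (according to Table 9) and analyzed using Mantel-Haenszel methodology".

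**The concern.** One checkbox cannot record both diseases, so Tables 5 and 9 contradict each other. A derivation table exists to be programmed as written. If this row is, the subgroup labelled chronic heart failure becomes a mixture: patients with heart failure as main diagnosis plus patients with renal failure. Patients with heart failure only as a comorbidity mostly fall into the comparison category, so both sides of the subgroup contrast are contaminated.

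The subgroup risk differences, the interaction p-value and the forest-plot entry would then describe a different population from the one named in the objectives. The Mantel-Haenszel version takes its categories from the same table, so it repeats the error and gives no check on it. The independent reproduction in section 6.7 is stated for the analysis of the primary outcome in the FAS and PPS, which most naturally means the main comparison and not the subgroups.

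**Working it through.** **Codes side by side**

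| Subgroup in Table 9 | Checkbox used in Table 9 | Label of that checkbox in Table 5 | Agree? |
|---|---|---|---|
| Diabetes | `comorbidities__5` | Diabetes | yes |
| Chronic heart failure | `comorbidities__9` | Chronic renal failure | **no** |
| COPD | `comorbidities__7` | COPD | yes |
| Cancer | `comorbidities__8` | Active cancer | yes |

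Three of the four match, so Table 9 uses the numbering of Table 5. A text-extraction fault is unlikely: the code appears in two separate cells of the row, and Table 5 runs in sequence from 1 to 13.

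**Could it be intended?** The COPD row pairs a main diagnosis with the checkbox of the same disease. The cancer row does nearly the same, joining neoplasm as main diagnosis to "comorbidities__8==checked" (active cancer). Only the heart failure row joins two different organ diseases. No renal subgroup is listed in sections 1.2 or 6.3.4.

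**Which patients are misclassified.** Write M for heart failure as main diagnosis, C1 for `comorbidities__1` checked and C9 for `comorbidities__9` checked. The rule by the Table 5 codes is M or C1; the printed rule is M or C9. When M = 1 (four combinations) both rules include the patient. When M = 0:

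| C1 | C9 | M or C1 | M or C9 (printed) | Result |
|---|---|---|---|---|
| 0 | 0 | out | out | same |
| 1 | 1 | in | in | same |
| 0 | 1 | out | in | wrongly added |
| 1 | 0 | in | out | missed |

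Two of the eight combinations differ, one in each direction. This part needs no assumptions.

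**Illustrative size.** The only input from the SAP is N = 1,380 (section 2.3). The rest are assumptions:

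- a, heart failure as main diagnosis: 8% (range 5 to 10%)
- c, heart failure as comorbidity only: 20% (15 to 30%)
- R, renal failure overall: 25% (15 to 35%)
- k, ratio of renal failure frequency with versus without heart failure: 1.5 (1 to 2)

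Formulas: T = a + c; r0 = R / ((1 − T) + kT); r1 = k·r0; added = N(1 − T)r0; missed = N·c(1 − r1).

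Central values:

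- T = 0.28
- r0 = 0.25 / (0.72 + 0.42) = 0.2193 and r1 = 0.3289
- added = 1,380 × 0.72 × 0.2193 = 217.9
- missed = 1,380 × 0.20 × 0.6711 = 185.2

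Extremes over the assumed ranges:

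- added: 88.7 (a 0.10, c 0.30, R 0.15, k 2) to 386.4 (a 0.05, c 0.15, R 0.35, k 1)
- missed: 86.3 (a 0.05, c 0.15, R 0.35, k 2) to 351.9 (c 0.30, R 0.15, k 1)

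**Second set-up.** Assume main-diagnosis heart failure in 5 to 10% and, among the remaining patients, comorbid heart failure in 15 to 30% and renal failure in 15 to 35%, independent of each other. The printed rule then captures about 28 to 63% of the true heart failure patients, and about 26 to 60% of those it flags truly have the disease.

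**The case against.** The best counter-argument concerns weight. This is one wrong index in one of nine subgroups. The row label, the subgroup list and the objectives all say chronic heart failure, and Table 5 supplies the likely code, so an attentive programmer might notice. That is fair, and it limits the seriousness, but it does not make the printed rule right.

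Several narrower points stand:

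- If the fields are treated as baseline, as section 5.5 does, the printed rule still gives a randomised comparison, only in a mislabelled, mixed group. Where the treatment effect is the same in all these patients, the estimate is not systematically shifted. No direction or size of distortion can be shown from the SAP.
- The patient counts rest on assumed prevalences and have wide ranges. The contradiction does not depend on them.
- Table 10 in section 7 records subgroup changes such as "Subgroups cancer, living place, living status and health insurance" and says nothing of heart failure. This is thin evidence, because that table lists departures from the protocol and not derivation codes.
- Section 6.7 does not expressly exclude subgroup analyses of the primary outcome from the second statistician's work. Someone working from the same Table 9 could, however, repeat the slip.
- The data dictionary is not at hand, so Table 5 might be the table in error. Even then the two tables conflict and one must be changed.

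**Conclusion.** The contradiction is plain on the face of the SAP, and nothing else in the document corrects it. Going by Table 5, the comorbidity half of the chronic heart failure rule points to the wrong disease; the main-diagnosis half is sound. Followed literally, the rule misclassifies patients in both directions, by roughly 200 each way of 1,380 at the assumed central prevalences. A subgroup named in the objectives would be reported for the wrong patients in both the regression and the Mantel-Haenszel analyses. The primary analysis, sample size, secondary outcomes and other subgroups are untouched. It should be fixed, but it does not threaten the trial's main conclusion.

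**What to change.** Look up the heart failure and renal failure checkboxes in the eCRF data dictionary. If Table 5 is confirmed, replace `comorbidities__9` by `comorbidities__1` in both the variable and the categorization cells of the chronic heart failure row of Table 9. If the dictionary instead supports Table 9, correct Table 5. Make the change before database lock: section 2.6 starts the analysis after it, and a later correction could look driven by the results.

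The cost is one look-up and one variable name in two cells. No new data are needed, no other analysis changes, and no power or information is lost.

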2.2 Randomization

Allocation of patients is done when all inclusion and exclusion criteria are satisfied. Patients are randomly assigned in a ratio of 1:1 to one of two treatment arms:

- 1) Transitional care (intervention) or
- 2) Usual care (control).

Allocation of patients is done with the data management system (REDCapTM) that also hosts the electronic case report forms (eCRFs). Allocation is stratified by:

- Discharge site (Hôpital Fribourgeois, Centre hospitalier Bienne, CHUV Lausanne, Hôpital neuchâtelois)
- Readmission risk category according to the simplified HOSPITAL score (intermediate vs high risk, i.e. a HOSPITAL score of 4 or 5 vs ≥ 6)

The readmission risk category is documented on eCRF “Eligibility” by variable `strat_1`, the discharge site is coded via the patient ID. The random allocation is performed centrally within the data management system using permuted block with random block sizes of 2, 4 and 6. Investigators receive the allocation only after the eCRF “Eligibility” has been completed. The allocation is documented by variable `alloc_a_group` on eCRF “Eligibility”.

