2.3 Sample size

Because we will target patients at higher risk of readmission, we hypothesize that the intervention could reduce the relative risk of readmission by 25%, i.e. more than the 18% reduction found in a recent meta-analysis where patients were mostly not at high risk for readmission. Based on previous findings, the expected 30-day readmission and death rate for patients at intermediate or high risk according to the simplified HOSPITAL score is around 27%. Allowing for 10% loss to follow-up, we determine that we will need 1,380 patients for the study to have 80% power, i.e. 690 in each arm.

The intervention phase (randomized controlled trial) will be restricted to the eligible patients who are at intermediate to high risk of 30-day readmission according to the simplified HOSPITAL score, i.e. $\geq 4/13$ points. We estimate to have around 18,000 patients discharged during the 20-month study period, 30% of which (5,400) will be at higher-risk for a 30-day readmission or death. This should be enough to reach the targeted sample size within the study time frame.

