4.2 Confidence intervals and p-values

A level of statistical significance of 5% will be used. All statistical testing will be two-sided. All tests will be accompanied by an effect measure (transitional care vs usual care) with a 95% confidence interval (95% CI).

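### Wherever the Poisson fallback is used for a subgroup, the planned likelihood ratio test for interaction has about half its nominal 5% size (about a third for site)

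*SAP*

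**What the plan says.** Section 6.3.4 analyses the primary outcome in nine subgroups: readmission risk group, site, four diseases, living place, living status and insurance. Each model contains treatment, subgroup, their interaction and the randomisation factors. The first choice is a binomial model with identity link. If that is not possible, the SAP continues: "Otherwise, a Poisson model with identity link and robust standard errors (leading to risk differences") and gives a binomial logit model, reported as odds ratios, as the alternative. Either of these is only to be considered; neither is fixed.

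The interaction test is then set once, without distinguishing the models: "Models with and without interaction will be compared using a likelihood ratio test". Its result is the reported interaction p-value, and everything goes into a forest plot.

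Section 4.2 gives the standard that this p-value should meet: "A level of statistical significance of 5% will be used", and "All statistical testing will be two-sided". It also wants every test accompanied by an effect measure with a 95% confidence interval.

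**The concern.** Robust standard errors are specified for the Poisson model because its variance is wrong for a yes/no outcome. They repair the standard errors and the Wald intervals. A likelihood ratio test compares two maximised Poisson likelihoods and never uses the robust covariance matrix, so the interaction p-value rests on the variance that the robust errors were meant to replace.

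Because p exceeds p(1-p), the statistic is too small and the p-value too large. For a subgroup analysed this way, a real difference in effect is more easily missed. The interval and the p-value shown together would rest on different variances. If some subgroups were fitted by binomial and others by Poisson models, their interaction p-values would not be on the same footing.

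**Working it through.** **Inputs from the SAP.** Two-sided 5% level (section 4.2). Allocation: "Patients are randomly assigned in a ratio of 1:1" (section 2.2). Control risk: "readmission and death rate for patients at intermediate or high risk according to the simplified HOSPITAL score is around 27" per cent (section 2.3). Effect: "the intervention could reduce the relative risk of readmission by 25" per cent (section 2.3). Four sites (section 2.2), so the site interaction has 3 df; the other eight subgroups are two-level in Table 9, so 1 df.

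**Step 1: reproduce the plan's own figure.** Intervention risk = 0.27 × 0.75 = 0.2025; difference 0.0675; average risk 0.23625. With pooled variance and no continuity correction:

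n per arm = [1.960 × √(2 × 0.23625 × 0.76375) + 0.8416 × √(0.27 × 0.73 + 0.2025 × 0.7975)]² / 0.0675² = 620.5, so 621.

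621 / 0.90 = 690 per arm, 1,380 in total. This matches section 2.3: "Allowing for 10% loss to follow-up, we determine that we will need 1,380 patients for the study to have 80% power, i.e. 690 in each" of the two groups. The planned rates are therefore the right basis for the next step.

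**Step 2: true size of the Poisson likelihood ratio test.** With working variance p and true variance p(1-p), the statistic under no interaction is approximately (1-p) × chi-square. With nominal critical value c, the true size is P(chi-square > c / (1-p)).

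| Risk p | 1 df: 3.841/(1-p) | size | 3 df: 7.815/(1-p) | size |
|---|---|---|---|---|
| 0.15 (assumed) | 4.519 | 3.4% | 9.194 | 2.7% |
| 0.2025 | 4.817 | 2.8% | 9.799 | 2.0% |
| 0.23625 | 5.030 | 2.5% | 10.232 | 1.7% |
| 0.27 | 5.262 | 2.2% | 10.705 | 1.3% |
| 0.40 (assumed) | 6.402 | 1.1% | 13.025 | 0.5% |

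At the average risk, a 1-df result that should sit exactly at p = 0.05 gives a statistic of 0.76375 × 3.841 = 2.934 and is reported as p = 0.087.

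**Step 3: simulation.** N = 1,380, additive risks, no interaction, 8,000 trials per scenario. Assumed, not in the SAP: 35% high risk, site shares 35/25/20/20%, subgroup prevalence 30% or 10%, modest subgroup, risk-group and site effects. The Poisson model was fitted in every trial, whether or not the binomial one failed.

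| Scenario | Poisson LR test | Robust Wald | Binomial identity LR test |
|---|---|---|---|
| 30% prevalence, covariate effects | 2.5% | 5.4% | 5.1% |
| 30% prevalence, no covariate effects | 2.6% | 5.2% | 5.0% |
| 10% prevalence, covariate effects | 2.3% | 5.7% | 5.2% |
| Site interaction, 3 df | 1.7% | 4.9% | 4.7% |

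A separate simulation gave 2.9% and 2.6% for the Poisson test at 30% and 10% prevalence, against 5.6% and 5.9% for the robust Wald test.

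**Step 4: power.** For an assumed true interaction of 15 points and a subgroup of 40%, two simulations gave 77% and 81% for the Poisson likelihood ratio test, against 86% and 89% for the robust Wald test. This agrees with theory: the test needs |Z| > √5.030 = 2.243 instead of 1.960. A robust test with 86% power has mean Z = 1.960 + 1.080 = 3.040, and Φ(3.040 - 2.243) = 79%.

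**Step 5: how often the first-choice model fails.** Plain iterative fitting of the binomial identity model, counting any fitted risk outside 0 to 1 as failure:

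- Interaction with risk group (40% high risk; control risks 23%/33%, or 27% in both): 0 of 4,000 in each.
- Two-level subgroup of 30%, and the site interaction: 0 of 2,000 in each.
- Subgroup of 10%: from 0.2% up to 1.1% (91 of 8,000), depending on the assumed effects.
- Subgroup of 5%: 1.6% if it has higher risk, 19% if it has lower risk.

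**The case against.** The strongest reply is that the flaw may never surface. It needs two things: the binomial identity model must fail, and the analyst must choose Poisson over logit, for which the likelihood ratio test is valid. Step 5 shows that the first condition is rare except for a very small subgroup with low risk. In such a subgroup the shortfall in size is also smaller, because it shrinks as p falls (3.4% at an assumed risk of 15%). The error is conservative, so it cannot produce a false subgroup claim. The power example assumes an interaction more than twice the planned overall effect of 6.75 points. The SAP also plans a Mantel-Haenszel homogeneity test for every subgroup, which does not use the Poisson likelihood.

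Most of this stands and limits the point. A reader might infer that identity-link models often fail to converge, so that the fallback will probably be used and all nine interaction p-values, including the stated objective of intermediate versus high risk, will have the wrong size. The documents do not support that. They give no subgroup prevalences, and at the planned rates the risk-group model never failed in simulation, so its p-value would come from the valid binomial test.

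What does not stand is the idea that the matter is covered elsewhere. The Mantel-Haenszel test is labelled secondary, is not stratified for the randomisation factors, and does not replace the reported interaction p-value. A fallback that the SAP writes down in advance needs a valid test.

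**Conclusion.** The point holds in a conditional form. Section 6.3.4 as written attaches an invalid p-value to one of its permitted models. Where the Poisson model is used, the nominal 5% interaction test has a true size of about 2.5% with 1 df and about 1.7% for site at the planned average risk. In the power example it loses about 8 to 9 percentage points.

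The size result depends only on the outcome risk and the degrees of freedom. The power and convergence figures also rest on assumed prevalences, site shares and covariate effects. The 2.5% is the size of that one test, not of the whole procedure that starts with the binomial model.

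The likelihood ratio test is sound for both binomial models. The primary analysis and the secondary outcomes are not affected. This is a minor but clear correction to a subgroup rule.

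**What to change.** Add one sentence to section 6.3.4: the likelihood ratio test applies to the binomial models (identity or logit link); if the Poisson model is used, the interaction p-value comes from a Wald test based on the robust covariance matrix, as a joint 3-df Wald test for site. The p-value and the intervals then share one variance. In the simulations this brought the size to between 4.9% and 5.9%, slightly above nominal in the smaller subgroups. It also helps to state in the forest plot which model was used for each subgroup.

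The odds-ratio fallback need not be replaced by standardised risk differences from the logit model. That would be a preference about the effect measure and is not needed to correct the test.

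The cost is one sentence, written before results are seen, with no change to data, design or sample size.
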